## PROTOCOL SUMMARY

Title of Study	Prospective Evaluation to Characterize the Real-World Performance of the EMBOVAC™ Aspiration Catheter for Neurothrombectomy: A Post-Market Clinical Follow-up Trial.	
Short Title	PERFECT	
Study Sponsor	CERENOVUS [name]	
Study Device	EMBOVAC™ Aspiration Catheter	
Indication	The EMBOVAC™ Aspiration Catheter is indicated for general intravascular use in the neuro vasculature. The catheter can be used to facilitate introduction of diagnostic or therapeutic agents and is also intended for use in removal/aspiration of emboli and thrombi from selected blood vessels in the neuro vasculature.	
Study Design	Prospective, multi-center, single arm, post-market clinical follow-up study.	
Sample Size	Approximately 100 subjects will be enrolled.	
Number of Sites	Approximately 10 institutions primarily in Europe.	
Study Duration	Start Date: 2020	End Date: 2022
Study Procedures	
EMBOVAC™ Aspiration Catheter is used with ADAPT (A Direct Aspiration, First Pass Technique) as the first attempted device/technique for mechanical thrombectomy in the subject.
 
The study evaluation time points follow the site's standard of care and include:
 
 
1. Study Procedure
 
2. 24 Hour follow-up (+/- 12 hrs)
 
3. 7 Day / Discharge follow-up (-1/+7 days) (whichever comes first)
 
4. 90 Day Follow-up (+/- 14 days)
 
	
Primary Objective	The primary objective of this Post-Market Clinical Follow-Up (PMCF) study is to characterize the performance of the EMBOVAC™ Aspiration Catheter in the treatment of acute ischemic stroke in a real-world clinical setting.	

Secondary Objective	The secondary objective is to confirm the benefit of a 'system approach' using Cerenovus products (e.g., distal access catheter, balloon guide catheter) which have been designed for use together in the treatment of acute ischemic stroke.
Primary Endpoint	Proportion of patients having successful revascularization, defined as number of subjects achieving a modified Thrombolysis in Cerebral Infarction (mTICI) score of $\geq 2b$ at the end of the procedure, as determined by Core Lab.

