## SCHEDULE OF ASSESSMENTS

**Table 1 Schedule of Assessments**

Assessments	Enrollment				Follow-up	
	Baseline	Procedure	24hrs post-procedure (+/- 12 hrs)	7 days/ discharge (- 1/+7 days) (whichever comes first)	📞 90 Day Follow-up (+/- 14 days)	Unscheduled (6)
Eligibility Screening	X	X	X	X		
Informed Consent	Patient consent may be obtained up to 45 days post procedure					
Demographics and Medical History	X					
IV t-PA administration	O					
Imaging 	X		X			O
NIH Stroke Scale (NIHSS)	X 		X 	O	O	O
Modified Rankin Scale (mRS)	X 			O	X 	O
Angiography 		X				
Review of Reportable AEs 		X	X	X	X	X
Clot Collection 		X				
Health Economics Data Collection		X	X	X	X	X

(1) Imaging will be sent to independent Imaging Core Lab for review

(2) Procedural angiography will be sent to Imaging Core Lab for review

(3) Per pass clot collection to be sent to Clot Analysis Lab for processing

(4) If more than one NIHSS was performed during this time period, select the worst (highest) value

(5) To be administered pre-procedure by a qualified evaluator; pre-stroke mRS should reflect the subject's condition just prior to the stroke onset. For example, if the subject was hospitalized during stroke onset, the subject's reason for hospitalization should be taken into account when evaluating the subject's pre-stroke mRS

(6) Assessments should be completed for unscheduled visits from the time of Discharge up to (but not including) the 90-day Follow-up, where imaging, NIHSS or mRS is performed as part of stroke management care for the subject

(7) The 90 day mRS must be performed by a qualified independent evaluator. This may be performed by phone per the site's SOC.

(8) AEs will be reported and recorded (via eCRF) if any of the following apply: (a) The event is neurological in nature (b) The event is a serious adverse event (SAE) (c) AE where causality is related to the device or procedure.

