### 3.2.3. Safety Endpoints

1. **Device related serious adverse events within 90 days** –where the EMBOVAC™ Aspiration Catheter caused, or cannot be ruled out as having caused, an event that has resulted in any of the consequences characteristic of an SAE. Device relatedness will be adjudicated by an independent CEC.
2. **Symptomatic Intracerebral Hemorrhage (sICH) at 24 hours specified according to the Heidelberg Bleeding Classification** – adjudicated by an independent CEC - defined as a new intracranial hemorrhage as detected by brain imaging, measured 24 hours after intervention [18], associated with any of the following:
  - $\geq 4$  points total NIHSS at the time of diagnosis compared to immediately before worsening. Note that a 4 points change is not compared with the baseline admission NIHSS score but instead to the immediate pre-deterioration neurological status
  - $\geq 2$  point in one NIHSS category. The rationale for this is to capture new hemorrhages that produce new neurological symptoms, making them clearly symptomatic but not causing worsening in the original stroke territory. For example, a new remote hemorrhage in the contralateral occipital lobe may cause new hemianopia that is clearly symptomatic, but the subject will not have worsening of  $\geq 4$  points on the NIHSS score
  - Leading to intubation/hemicraniectomy/EVD placement or other major medical/surgical intervention
  - Absence of alternative explanation for deterioration
3. **NIHSS at 24 hours post procedure** – NIHSS will be measured at 24 hours and compared to the baseline score.
4. **90 Day All-Cause Mortality** – All mortality regardless of cause at 90 days post-procedure.

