7.3	Demographic and Baseline Characteristics.....	7
7.4	Procedural Characteristics.....	7
7.5	Primary and Secondary Endpoints.....	7
7.5.1	Primary Endpoint.....	8
7.5.2	Secondary Endpoints	8
7.5.2.1	Secondary Effectiveness Endpoints.....	8
7.5.2.2	Secondary Safety Endpoints.....	9
7.6	Health Economic Endpoints.....	10
7.7	Clot Analysis	10
7.8	Analyses of Adverse Events (AEs).....	11
7.9	Plans for Interim Analyses	12
7.10	Handling of Missing Data	12
7.11	Sensitivity Analyses.....	12
7.12	Subgroup Analysis.....	12
7.13	Additional Analyses.....	13
7.14	Changes from Planned Analyses	13

1 Study Design

This is a prospective, multi-center, single-arm, post-market clinical follow-up study that will enroll approximately 100 subjects at approximately 10 sites primarily in Europe, with clot collection for follow-on histopathological analysis. Subjects will be included in the study for a period of 3 months after the procedure, including follow up visits at 24 hours, 7 days (or discharge) and 90 days after the procedure.

2 Treatment Assignment

This is a single arm study and all enrolled subjects are intended to be treated with the study device, the EMBOVAC Aspiration Catheter.

3 Interval Windows

Study reports will be summarized using analysis visits as defined below.

- 24 Hours post-procedure (-12 to +48 hours)
- 7-Day/Discharge (-1 to +7 days)
- 90-day follow-up (± 15 days)

The study schedule is to be adhered to as closely as possible for all subjects. Data will be summarized by scheduled visit. Measurements outside the analysis windows will be considered as missing in the analysis. In the case of repeated measurements taken at the same visit, the most recent measurement with non-missing values will be used unless specified otherwise.

4 Levels of Significance

No hypothesis tests are planned in the study. All confidence intervals will be reported at a two-sided 95% confidence level. These confidence intervals will not be used for statistical inferences, but for clinical reference purpose and are intended to convey precision in the estimates.

5 Analysis Sets

The following analysis sets are defined in the study:

- **Modified Intent-to-Treat (mITT) Analysis Set**

The mITT analysis set will consist of enrolled subjects who have received treatment (at least one pass; a pass being defined as use of aspiration followed by evaluation of revascularization with angiography) with the study device.

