7.1 General Conventions

Descriptive summary statistics will be presented for all endpoints. The number and percentage of subjects will be summarized for categorical variables. Unless specified otherwise, percentages will be based on subjects with non-missing values. Descriptive statistics for continuous variables will include the number of subjects, mean, standard deviation, median, first quartile (Q1), third quartile (Q3), minimum and maximum. All statistical analyses will be performed using SAS® Studio, Version 9.4 or later.

- **Baseline**

Unless specified otherwise, the last non-missing measurement collected during the baseline visit is considered as the baseline measurement (prior to the start of the index procedure).

- The pre-stroke mRS score will be considered as the baseline mRS score.
- The highest (worst) NIHSS score will be considered as the baseline NIHSS score should a subject have more than one non-missing NIHSS score at baseline.

- **Study Day**

Unless specified otherwise, study day will be calculated as the difference between the event/assessment date and index procedure date, i.e., event/assessment date - index procedure date, and the date of index procedure is considered as Day 0.

- Stroke onset date and time

Stroke onset date and time is defined as follows:

- For witnessed stroke, the stroke onset date and time as reported from the case report form (CRF) will be used;
- For un-witnessed stroke, the date and time when the subject was last seen well from CRF will be used.

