7.5.2.2 Secondary Safety Endpoints

Device-related SAEs and all-cause mortality, Kaplan-Meier analysis (using product limit estimates) will be applied. Kaplan-Meier event rate and its associated two-sided 95% CIs using log-log transformation will be reported, the estimate of standard error will be computed using Greenwood's formula.

- **Devices related serious adverse events (SAEs) within 90 days of follow up as determined by an independent Clinical Events Committee**

Kaplan-Meier analysis will be performed to analyze the device related SAE rate within 90 days. Device related SAEs are considered as events; where the event date is the date of first event. Subjects without events will be censored at the date of last contact. The event rate at 90 days with associated 95% CIs will be provided. Device related SAEs beyond 90 days will be listed.

- **sICH at 24h post procedure specified according to the Heidelberg Bleeding Classification (HBC) as determined by an independent Clinical Events Committee**

sICH at 24 hours post procedure as specified by HBC will be assessed. The number and percentage of subjects with events will be summarized with CIs.

- **NIHSS at 24h post procedure**

The observed NIHSS total score at 24 hours post-procedure and changes from the baseline score will be summarized.

- **90 Day All-Cause Mortality**

Kaplan-Meier analysis will be performed to analyze all-cause mortality within 90 days. All-cause mortality is considered as the event; where the event date is the date of mortality. Subjects without events will be censored at the date of last contact. The event rate at 90 days with associated 95% CIs will be provided. Deaths beyond the 90 days will be listed.

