7.13 Additional Analyses

- Protocol deviations

The number of deviations, the number and percentages of subjects with any protocol deviation will be summarized overall and by deviation category.

- Device malfunctions/deficiency

Subjects with at least one device malfunctions/deficiency will be listed.

- NIH Stroke Scale (NIHSS) total score

The NIHSS total score and change from baseline will be summarized at the scheduled visits with observed data.

- mTICI scores

All mTICI scores will be summarized by pass and at the end of study procedure using the assessments from the core lab.

- mRS scores

mRS scores by categories of 0, 1, 2, ..., 6 will be summarized at scheduled visits using mITT analysis set. A shift table of mRS score from baseline to 90-day follow-up will be summarized as well.

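### The SAP applies the protocol's worst-NIHSS rule at baseline but not at 24 hours, and widens the 24-hour window without saying why

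*SAP*

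**What the plan says.** **Endpoint.** Protocol 3.2.3 lists 24-hour NIHSS as a safety endpoint: "NIHSS will be measured at 24 hours and compared to the baseline score".

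**Repeated scores, protocol.** In Table 1 the NIHSS cells at baseline and at 24 hours both carry footnote 4: "If more than one NIHSS was performed during this time period, select the worst (highest) value". The optional later NIHSS cells do not carry it.

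**Repeated scores, SAP.** Section 3 sets the default: "In the case of repeated measurements taken at the same visit, the most recent measurement with non-missing values will be used unless specified otherwise". Section 7.1 makes an exception: "The highest (worst) NIHSS score will be considered as the baseline NIHSS score" when a subject has several. That exception is confined to baseline. Two places use the 24-hour score. Section 7.5.2.2 says "The observed NIHSS total score at 24 hours post-procedure and changes from the baseline score will be summarized" and section 7.13 says "The NIHSS total score and change from baseline will be summarized at the scheduled visits with observed data". Neither says which score to take when there is more than one.

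**Window.** The protocol (Summary, Table 1 and section 7.4) gives ±12 hours around 24 hours. SAP section 3 gives -12 to +48 hours and treats values outside its windows as missing.

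**Declared changes.** SAP 7.14 declares and explains one change, to the 90-day mRS window. It mentions neither the 24-hour selection rule nor the 24-hour window.

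**The concern.** One protocol footnote covers both ends of the change score, and the SAP carries over only the baseline end. A programmer working from the SAP would subtract the worst baseline score from the latest 24-hour score, so one difference would mix two selection rules. Taking the maximum at baseline and the last value at follow-up tends to make patients look more improved than applying one rule at both visits.

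The window is a second, separate departure. It changes which scores count as 24-hour scores, and it interacts with the selection rule, because a later cut-off gives a most-recent rule more late scores to choose from.

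What is at stake is a reported estimate for a named safety endpoint. No hypothesis test, sample size or primary result depends on it. But in a study with no tests the descriptive estimates are the result, and both documents plan interim descriptive reports for regulatory submissions.

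**Working it through.** The plan gives no figure for this endpoint. Its only calculation, the primary-endpoint margin of error, reproduces (1.96 × √(0.8 × 0.2 / 95) = 8.0%) and is unaffected.

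**1. Direction in a fixed window.** Write Bmax and Blast for the worst and last baseline scores, and Fmax and Flast for the worst and last 24-hour scores.

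- Protocol change = Fmax − Bmax
- SAP change = Flast − Bmax
- SAP minus protocol = Flast − Fmax ≤ 0, and 0 with a single 24-hour score
- Against a last/last rule (a reference only; neither document proposes it for NIHSS): SAP minus last/last = Blast − Bmax ≤ 0, and 0 with a single baseline score

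Since a lower NIHSS is better, the SAP change is never less favourable than either.

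**2. Illustrative size.** The documents give neither the within-patient SD (s) nor the share of subjects with repeats, so both are assumed. For two independent normal readings with no trend, E[max] − mean = s/√π:

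- s = 1: 0.56 points
- s = 2: 1.13 points
- s = 3: 1.69 points

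Mean change by number of scores at each visit, with s = 2 and no true change:

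| Baseline, 24 h | Protocol worst/worst | SAP | Last/last |
|---|---|---|---|
| 1, 1 | 0 | 0 | 0 |
| 2, 1 | −1.13 | −1.13 | 0 |
| 1, 2 | +1.13 | 0 | 0 |
| 2, 2 | 0 | −1.13 | 0 |

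The SAP departs from the protocol rule only in the two rows with a repeated 24-hour score. These are distances from the protocol rule, not bias against the true change: in the third row it is the protocol rule that moves away from zero.

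If the mean falls by d between the two 24-hour scores, E[worst − last] = d·Φ(d/(s√2)) + s√2·φ(d/(s√2)). For s = 2 and d = 2 this is 2 × 0.760 + 2.828 × 0.311 = 2.40. Over s = 1 to 3 it runs from 2.05 to 2.88 for d = 2, and from 0.05 to 0.88 if scores rise by 2 instead.

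If 10% to 50% of subjects have two 24-hour scores, the cohort mean shifts by:

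- no trend: 0.1 × 0.56 = 0.06 up to 0.5 × 1.69 = 0.85 points
- d = 2: 0.1 × 2.05 = 0.21 up to 0.5 × 2.88 = 1.44 points

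**3. Window width.**

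- Protocol: 24 − 12 = 12 h to 24 + 12 = 36 h, which is 24 h wide.
- SAP, both offsets from 24 h: 12 h to 24 + 48 = 72 h, which is 60 h wide, or 60/24 = 2.5 times the protocol's.
- SAP, if the upper bound meant 48 h after the procedure: 12 h to 48 h, which is 36 h wide, or 1.5 times.

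It is wider on either reading.

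**4. The window can reverse the direction.** Take an invented subject with baseline 16, a score of 8 at 24 h and 14 at 60 h, the last two both counted in the SAP's 12 to 72 h window.

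- Protocol: only the 24 h score is in window, so 8 − 16 = −8.
- SAP: 14 − 16 = −2.
- Worst-score rule applied to the SAP's wide window: max(8, 14) − 16 = −2.

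The certainty in step 1 therefore holds only for a fixed window, and correcting the rule alone does not restore the protocol's value.

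**The case against.** The strongest objection is that footnote 4 is a data-entry instruction. It sits in the schedule of assessments and tells the site which score to pick. If sites enter one 24-hour score, already the worst, the SAP default has nothing to choose between and the difference is zero. This stands as a limit on the effect. It does not settle the matter, because no document says how many scores the eCRF holds, and SAP 7.1 itself allows for several baseline scores under the same footnote.

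The SAP also repeats the protocol's own analysis sentence for this endpoint (protocol 10.5.4.2.2), and its default yields to anything specified elsewhere, which might include the footnote. But the SAP never cites the footnote, and it wrote the rule out for baseline. On this reading the text is ambiguous, and the same sentence cures it.

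On the window, exclusion criterion 1 and protocol sections 7.1 and 14 screen out, or treat as eligibility deviations, assessments made outside protocol requirements before consent. Few late scores may therefore enter. That limits the window's reach, but not repeats within 12 to 36 h. A wider analysis window also retains data that would otherwise be missing, which could be a fair reason if the SAP stated it. The second reading of the upper bound is weak, since -12 can only count from 24 h and the neighbouring windows are offsets from nominal. The window is wider without that reading.

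Finally, the magnitudes rest on assumptions, and neurological harm is also captured through adjudicated sICH and reporting of neurological adverse events. Both points are accepted, and both hold the severity at minor.

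**Conclusion.** The concern holds and is minor. The SAP as written does not carry the protocol's worst-score rule to 24 hours and does not declare the departure. Followed literally, it can pair the worst baseline score with the latest 24-hour score on a secondary safety endpoint. In a fixed window the resulting change is equal to or more favourable than the protocol's.

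The real size is unknown. The per-subject and cohort ranges above assume normal, independent readings, an SD of 1 to 3 points, two 24-hour scores and a 10% to 50% share of subjects with repeats. If only one 24-hour score per subject reaches the database, the selection-rule difference is nil. The wider window is a separate undeclared departure of unknown direction, probably with small reach, and it can offset or reverse the selection effect. Confidence is moderate, mainly because the documents do not show how scores are recorded.

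**What to change.** - **Selection rule (SAP 7.5.2.2 and 7.13).** State that when a subject has more than one NIHSS in the 24-hour window the highest is used, citing protocol Table 1, footnote 4.
- **Window (SAP 3).** Use the protocol's ±12 hours for the main 24-hour NIHSS summary and keep the wider window as a sensitivity analysis. Alternatively, keep the wider window, give the reason and list it in SAP 7.14. In either case state the bounds as hours after the procedure.
- **Settle both together.** As the example shows, the worst-score rule in the wider window can still give a value other than the protocol's.

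The cost is one sentence for the rule and one for the window. No new data are needed and the protocol endpoint is unchanged. The downside is that any 24-hour scores taken after 36 hours move to the sensitivity analysis.

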7.1 General Conventions

Descriptive summary statistics will be presented for all endpoints. The number and percentage of subjects will be summarized for categorical variables. Unless specified otherwise, percentages will be based on subjects with non-missing values. Descriptive statistics for continuous variables will include the number of subjects, mean, standard deviation, median, first quartile (Q1), third quartile (Q3), minimum and maximum. All statistical analyses will be performed using SAS® Studio, Version 9.4 or later.

- **Baseline**

Unless specified otherwise, the last non-missing measurement collected during the baseline visit is considered as the baseline measurement (prior to the start of the index procedure).

- The pre-stroke mRS score will be considered as the baseline mRS score.
- The highest (worst) NIHSS score will be considered as the baseline NIHSS score should a subject have more than one non-missing NIHSS score at baseline.

- **Study Day**

Unless specified otherwise, study day will be calculated as the difference between the event/assessment date and index procedure date, i.e., event/assessment date - index procedure date, and the date of index procedure is considered as Day 0.

- Stroke onset date and time

Stroke onset date and time is defined as follows:

- For witnessed stroke, the stroke onset date and time as reported from the case report form (CRF) will be used;
- For un-witnessed stroke, the date and time when the subject was last seen well from CRF will be used.

7.2 Disposition of Study Subjects

The number and percentage of subjects in each analysis set will be provided, together with the summary of subjects who early terminated from the study with associated reasons.

Enrollment by site will be summarized for all consented subjects and each analysis set.

7.3 Demographic and Baseline Characteristics

All demographic profiles and baseline characteristics will be summarized descriptively for each analysis set as applicable, including but are not limited to:

- Demographics and baseline characteristics, including age at consent (years), sex, height (cm), weight (kg), body mass index (kg/m^2), systolic/diastolic blood pressure (mmHg), ethnicity, race, etc.
- Medical history
- Baseline stroke characteristics, including time to puncture since stroke onset (mins); use of intravenous tissue plasminogen activator (IV-tPA, yes or no), NIHSS score, pre-stroke mRS score (by category of 0, 1, ..., 5), etc.

7.4 Procedural Characteristics

Procedural characteristics will be summarized descriptively for each analysis set by pass and overall.

7.5 Primary and Secondary Endpoints

Modified Thrombolysis in Cerebrovascular Infarction (mTICI) scores will be summarized using the assessments from the independent core lab. Missing mTICI scores will be excluded from the analysis.

